6.2.3 Hepatotoxicity Stopping and Rechallenge Rules

Refer to [Section 11.7](#) for details regarding drug-induced liver injury guidelines, as specified in the *Guidance for Industry Drug-Induced Liver Injury: Premarketing Clinical Evaluation, July 2009*.

6.3 Preparation/Handling/Storage/Accountability

Guidance and information on preparation, handling, storage, accountability, destruction, or return of the investigational products (AMG 330 and pembrolizumab) during the study are provided in the IPIM.

6.4 Measures to Minimize Bias: Randomization and Blinding

6.4.1 Method of Treatment Assignment

Subjects who meet eligibility criteria will be assigned to treatment with AMG 330 in combination with pembrolizumab.

6.4.2 Blinding

This is an open-label study; blinding procedures are not applicable.

6.5 Treatment Compliance

Not applicable

6.6 Treatment of Overdose

Treatment of Overdose with AMG 330

The effects of overdose of this product are not known. The daily AMG 330 dose may be up to 10% lower or higher in order to account for possible pump inaccuracies. A dose of up to 10% higher than the intended dose may not require specific intervention.

In case of overdose or medication error, the infusion should be immediately stopped. Consultation with the sponsor is strongly recommended for prompt reporting of clinically apparent or laboratory adverse events possibly related to overdosage. Consultation with the sponsor is also strongly recommended even if there are no adverse events, in order to discuss the minimal duration of dose interruption. If the overdose results in clinically apparent or symptomatic adverse events, the subject should be followed carefully until all signs of toxicity are resolved and the adverse event(s) should be recorded/reported per [Section 11.4](#). Resumption of AMG 330 is possible after consultation with the sponsor and should adhere to the guidelines in [Section 6.2.2.1](#).

A dose of > 10% higher than the intended AMG 330 dose will be considered clinically important and classified as a serious adverse event under the criterion of “other medically important serious event” per [Section 11.4](#).

Refer to the [AMG 330 Investigational Brochure](#) for further information.

Treatment of Overdose With Pembrolizumab:

For this study, an overdose of pembrolizumab will be defined as any dose of 1000 mg or \geq 5 times the indicated dose.

No specific information is available on the treatment of overdose of pembrolizumab. In the event of overdose, the participant should be observed closely for signs of toxicity. Appropriate supportive treatment should be provided if clinically indicated.

6.7 Prior and Concomitant Treatment

6.7.1 Prior Treatment

Prior therapies that were being taken/used from the time of initial diagnosis of AML through the signing of informed consent will be collected.

6.7.2 Concomitant Treatment

Throughout the study, investigators may prescribe any concomitant medications or treatments deemed necessary to provide adequate supportive care except for those listed in [Section 6.1.7](#).

Concomitant therapies are to be collected from signing of informed consent through the end of the safety follow-up period.

Oxygen administration as supportive measure is permitted during study treatment.

Hydroxyurea for 7 days at a dose of 1 – 10 g/day is recommended prior to the first cycle of investigational product treatment for subjects with high WBC ($> 15\,000$ cells/mcL). Administration of hydroxyurea after start of investigational product may be permitted after discussion with sponsor.

Premedication with dexamethasone is required prior to each AMG 330 treatment cycle and prior to each dose step for the prevention of CRS. Dexamethasone should be administered as a single IV dose (8 mg) within 1 hour of start of infusion or dose step, respectively.

In the case of re-start of infusion after an infusion interruption of > 24 hours, dexamethasone (8 mg IV) should be administered within 1 hour prior to re-start and within 1 hour prior to the dose step.

For administration of dexamethasone and tocilizumab after occurrence of CRS, follow guidance in [Section 6.8](#).

Approved

6.8 Specific Recommendations for Cytokine Release Syndrome, Tumor Lysis Syndrome, and Infection Prophylaxis

Cytokine Release Syndrome

Cytokine release syndrome (CRS) is clinically defined and may have various manifestations. There are no established diagnostic criteria. Signs and symptoms of CRS may include:

- Constitutional – fever, rigors, fatigue, malaise
- Neurologic – headache, mental status changes, dysphasia, tremors, dysmetria, gait abnormalities, seizure
- Respiratory – dyspnea, tachypnea, hypoxemia
- Cardiovascular – tachycardia, hypotension
- Gastrointestinal – nausea, vomiting, transaminitis, hyperbilirubinemia
- Hematology – bleeding, hypofibrinogenemia, elevated D-dimer
- Skin – rash

Subjects may be at an increased risk for CRS during the first few days following the initial infusion of AMG 330. Cytokine release syndrome may be life-threatening or fatal. Infusion reactions may be clinically indistinguishable from manifestations of CRS. Throughout the infusion with AMG 330, monitor subjects for clinical signs (eg, fever, tachycardia, dyspnea, tremors) and laboratory changes (eg, transaminase increase) which may be related to CRS.

Grading and management of CRS should be performed according to the guidelines provided in [Table 6-5](#) (based on the adopted grading system referenced in [Lee et al, 2014](#)).

Approved

Table 6-5. Grading and Management of Cytokine Release Syndrome

CRS Grade	Description of Severity ^a	Minimum Expected Intervention ^c	Instructions for Interruption of AMG 330
1	Symptoms are not life threatening and require symptomatic treatment only, eg, fever, nausea, fatigue, headache, myalgias, malaise	
 Administer symptomatic treatment (eg, paracetamol/ acetaminophen for fever, fluids for hypotension). Consider use of tocilizumab 4 mg/kg IV. Up to 3 additional doses can be given 8 hours apart, if needed. Monitor for CRS symptoms including vital signs and pulse oximetry at least Q2 hours for 12 hours or until resolution, whichever is earlier. 	N/A
2	
Symptoms require and respond to moderate intervention
 
 Oxygen requirement < 40%, OR Hypotension responsive to fluids or low dose of 1 vasopressor, OR Grade 2 organ toxicity or grade 3 transaminitis per CTCAE criteria 	
Administer:
 
 Symptomatic treatment (eg, paracetamol/ acetaminophen for fever; vasopressors for hypotension) Supplemental oxygen when oxygen saturation is < 90% on room air Intravenous fluids or low dose vasopressor for hypotension when systolic blood pressure is < 100 mmHg. Persistent tachycardia (eg, > 120 bpm) may also indicate the need for intervention for hypotension. Consider use of tocilizumab 8 mg/kg IV. Up to 3 additional doses can be given 8 hours apart, if needed. 
Monitor for CRS symptoms including vital signs and pulse oximetry at least Q2 hours for 12 hours or until resolution to CRS grade ≤ 1, whichever is earlier.
 
For subjects with extensive co-morbidities or poor performance status, manage per grade 3 CRS guidance below.
	
Institute medical management. If hypotension persists 8 hours after adequate medical management, de-escalate AMG 330 to 50% of the current dose for 24 hours. If symptoms persist, interrupt AMG 330. Refer to Section 6.2.2 for dose interruption guidelines. If symptoms improve to ≤ grade 1, re-escalate to the dose at which the CRS event previously occurred. If symptoms progress to grade 3 criteria, see row below.
 
Discontinue AMG 330 if there is no improvement to CRS ≤ grade 1 within 7 days. Do not administer pembrolizumab until symptoms improve to CRS grade ≤ 1

Page 1 of 2

Footnotes defined on next page of table

Approved

Table 6-5. Grading and Management of Cytokine Release Syndrome

CRS Grade	Description of Severity ^a	Minimum Expected Intervention	Instructions for Interruption of AMG 330
3	Symptoms require and respond to aggressive intervention 
 • Oxygen requirement $\geq 40\%$, OR • Hypotension requiring high dose^b or multiple vasopressors, OR • Grade 3 organ toxicity or grade 4 transaminitis per CTCAE v5 criteria 	Admit to intensive care unit for close clinical and vital sign monitoring per institutional guidelines. Administer tocilizumab 8 mg/kg IV. Up to 3 additional doses of 8 mg/kg of tocilizumab can be given 8 hours apart, if needed. Administer dexamethasone (or equivalent) IV at a dose maximum of 3 doses of 8 mg (24 mg/day). The dose should then be reduced step-wise.	Immediately interrupt AMG 330 until event resolves to CRS grade ≤ 1 . Discontinue AMG 330 if there is no improvement to CRS \leq grade 2 within 5 days or CRS \leq grade 1 within 7 days. Permanently discontinue AMG 330 if CRS grade 3 occurs at the initial step dose (ie, at MTD1). Do not administer pembrolizumab until symptoms improve to CRS grade ≤ 1 If recurrent grade 3 CRS, permanently discontinue pembrolizumab.
4	Life-threatening symptoms 
 • Requirement for ventilator support OR • Grade 4 organ toxicity (excluding transaminitis) per CTCAE criteria 	Admit to intensive care unit for close clinical and vital sign monitoring per institutional guidelines. Administer dexamethasone (or equivalent) IV at a dose maximum of 3 doses of 8 mg (24 mg/day). Further corticosteroid use should be discussed with the Amgen medical monitor. Additionally, tocilizumab should be administered at a dose of 8 mg/kg. Up to 3 additional doses can be given 8 hours apart, if needed.	Immediately stop the infusion and permanently discontinue AMG 330 therapy and pembrolizumab therapy.

Page 2 of 2

CRS = cytokine release syndrome; CTCAE = Common Terminology Criteria for Adverse Events;

IV = intravenous; MTD = maximum tolerated dose

^a Revised grading system for cytokine release syndrome (Lee et al, 2014).^b High dose vasopressors (all doses are required for ≥ 3 hours): norepinephrine monotherapy ≥ 20 μ g/min; dopamine monotherapy ≥ 10 μ g/kg/min, phenylephrine monotherapy ≥ 200 μ g/min, epinephrine monotherapy ≥ 10 μ g/min; if on vasopressin, vasopressin + norepinephrine equivalent of ≥ 10 μ g/min; if on combination vasopressors (not vasopressin), norepinephrine equivalent of ≥ 20 μ g/min.^c Investigators may also consider additional therapy, based on clinical judgment.

Re-start of Treatment after Infusion Interruption due to Cytokine Release Syndrome:

After interruption of AMG 330 infusion due to grade 3 CRS, the infusion may be re-started if all of the following criteria are met:

- Sponsor must be consulted prior to re-starting treatment
- The event has resolved to grade ≤ 1 prior to re-starting treatment

In case of an infusion interruption of > 24 hours, regardless of the reason for interruption, re-start of the infusion should be performed at the initial dose and dose steps should be performed prior to administering the interrupted dose. The dose level for each step and number of steps should be determined in consultation with the Sponsor prior to re-initiation of the infusion.

Tumor Lysis Syndrome

Subjects with AML and WBC < 10 000/ μ L are considered to be at low risk for tumor lysis syndrome. WBC > 10 000/ μ L and < 50 000/ μ L are considered to be at intermediate risk, and subjects with WBC > 50 000/ μ L are considered at high risk. This protocol requires that subjects have a maximum WBC count of 15 000/ μ L.

Additional high risk features include baseline uric acid > 450 μ g/L (7.5 mg/dL), serum creatinine > 1.4 mg/dL, and lactate dehydrogenase (LDH) greater than the upper limit of normal (ULN).

Patients with intermediate risk WBC count and elevated baseline uric acid (> 450 μ g/L), serum creatinine > 1.4 mg/dL, or LDH greater than ULN will be recommended to receive allopurinol prophylaxis. Typical dosing is 600-800 mg/day administered bid or qid and should begin 3 days before the first dose of study drug. Patients should be well hydrated and supplemented with IV fluid as clinically indicated.

For grade 3 and 4 tumor lysis syndrome, please see [Section 6.2.1](#) for DLT considerations.

Infection Prophylaxis

Subjects who may experience neutropenia for 7 days or longer are at a high risk for infectious complications. As appropriate, these subjects should be administered prophylactic antibacterial (eg, fluoroquinolones), antifungal and antiviral medications. These subjects should be monitored for early signs of breakthrough infections after the initiation of antibacterial therapy to prompt additional evaluation and possible therapy modification.

7. Discontinuation Criteria

Subjects have the right to withdraw from investigational product and/or other protocol-required therapies, protocol procedures, or the study as a whole at any time and for any reason without prejudice to their future medical care by the physician or at the institution.

The investigator and/or sponsor can decide to withdraw a subject(s) from investigational product, device, and/or other protocol-required therapies, protocol procedures, or the study as a whole at any time prior to study completion for the reasons listed in [Sections 7.1](#) and [Section 7.2.1](#).

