For an adverse event requiring dose modification, AMG 330 (and pembrolizumab for subjects receiving combination therapy) should be interrupted to allow recovery from the adverse event. Re-initiation of study drug cannot occur until adverse event decreases to grade ≤ 1 . In case of delayed recovery to grade ≤ 1 from treatment-related adverse events that results in a delay of treatment for > 21 days, the subject will not receive additional protocol-related therapy and will be removed from study unless discussed and agreed upon by the sponsor and investigators that it is in the best interest of the subject to receive additional therapy with AMG 330 and pembrolizumab (eg, if subject demonstrated response to therapy).

Assessment of causality (chronology, confounding factors such as disease, concomitant medications, diagnostic tests and previous experience with the agent) must be determined and documented by the investigator, prior to dose modification.

In case of grade 2 CRS, administration of AMG 330 can be continued on the currently tested dose level for 8 hours, and treatment provided to mitigate CRS symptoms. If symptoms do not improve to grade 1, the dose will be de-escalated by 50% for an additional 24 hours. If CRS grade 2 resolves to grade 1, the dose can be re-escalated back to the level being tested. If symptoms persist, AMG 330 infusion will be interrupted and pembrolizumab infusion will be delayed until symptoms improve to grade 1. If treatment is interrupted for < 24 hours, the interrupted AMG 330 dose can be resumed and re-escalated back to the tested dose level. If treatment is interrupted for > 24 hours, restart or repeat rules apply (see below).

In case of grade 3 CRS, AMG 330 treatment must be interrupted and pembrolizumab treatment postponed. Sponsor has to be consulted prior to a planned re-start. In case

of grade 4 CRS, treatment must be permanently discontinued. See [Section 6.8](#) for specific instructions for the management of CRS.

If the same grade 3 non-hematologic adverse event recurs despite a dose reduction, a second dose reduction versus discontinuation of the subject from further protocol therapy should be discussed and agreed upon the sponsor and investigators.

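### Table 6-5 lists fluids for hypotension as grade 1 CRS care, although fluid-responsive hypotension is a grade 2 criterion in the same table

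*Protocol*

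**What the plan says.** Protocol Table 6-5, in Section 6.8, is the study's tool for both grading and managing CRS. Section 6.2.1 sends readers to it for CRS grading instead of CTCAE.

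- **Grade 1 row.** The severity description covers symptoms that need only symptomatic treatment, and hypotension is not among its examples. The intervention cell nevertheless illustrates symptomatic treatment with "acetaminophen for fever, fluids for hypotension". It adds "Consider use of tocilizumab 4 mg/kg IV". The AMG 330 instruction is N/A, and pembrolizumab is not mentioned.
- **Grade 2 row.** One of three severity criteria joined by OR is "Hypotension responsive to fluids or low dose of 1 vasopressor". The intervention cell calls for "Intravenous fluids or low dose vasopressor for hypotension when systolic blood pressure is < 100 mmHg" and says "Consider use of tocilizumab 8 mg/kg IV". The AMG 330 instruction is "If hypotension persists 8 hours after adequate medical management, de-escalate AMG 330 to 50% of the current dose for 24 hours", then interruption if symptoms persist, and discontinuation if the event is not at grade 1 or below within 7 days. For pembrolizumab: "Do not administer pembrolizumab until symptoms improve to CRS grade" 1 or below.

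Section 6.2.2.1 gives the grade 2 dose rule with a slightly different trigger. AMG 330 may continue for 8 hours, and then: "If symptoms do not improve to grade 1, the dose will be de-escalated by 50% for an additional 24 hours".

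On which column sets the grade, footnote a of Table 6-5 ties only the severity column to the published grading system. Protocol Appendix 4 and SAP Section 9.6.2 both require CRS to be graded by that publication.

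**The concern.** The same clinical picture, CRS hypotension that is given fluids and responds, is grade 2 by the severity column and appears as grade 1 care in the intervention column. The examples also read like a deliberate ladder, with fluids for hypotension at grade 1 and vasopressors at grade 2, which makes the mistake easy.

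A site that works from the grade 1 row would omit the grade 2 dose step and the pembrolizumab hold, consider half the tocilizumab dose, and enter a lower grade in the data. Treatment-emergent and treatment-related adverse events are primary endpoints, and SAP Section 9.6.2 tabulates them by worst grade.

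Grade 1 is also the recovery threshold. Section 6.2.2.1 allows re-escalation once grade 2 CRS falls to grade 1, and Table 6-5 releases pembrolizumab at that level. A site that accepts fluid-dependent hypotension as grade 1 could declare recovery too early. Section 6.2.2.1 requires sponsor consultation before restart after grade 3 CRS but states no such requirement for this re-escalation.

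**Working it through.** The plan gives no figure on this point to reproduce. The check is a comparison of the two rows, followed by the size of the differences.

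**1. Which row applies.** The grade 2 hypotension criterion needs no other feature and has no pressure threshold. The threshold of 100 mmHg systolic appears only in the grade 2 intervention cell. Grade 1 severity does not mention hypotension. Fluid-treated, fluid-responsive CRS hypotension is therefore grade 2.

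**2. What differs between the rows.**

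| Item | Grade 1 row | Grade 2 row |
|---|---|---|
| AMG 330 | N/A | 50% dose for 24 h if unresolved at 8 h, then interruption |
| Pembrolizumab | no instruction | held until grade 1 or below |
| Tocilizumab to consider | 4 mg/kg | 8 mg/kg |
| Worst grade recorded | 1 | 2 |

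**3. Tocilizumab.** Per dose, 4/8 = 0.5. Both rows allow one dose plus up to 3 more. If the later doses are the same size, the maxima are 4 × 4 = 16 mg/kg and 4 × 8 = 32 mg/kg. Use is optional in both rows.

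**4. AMG 330 over the first 32 hours.** This takes the Section 6.2.2.1 trigger (no improvement to grade 1 at 8 hours) in a subject whose pressure is still maintained by fluids.
- Grade 2 rule: (8 × 1.0 + 24 × 0.5)/32 = 20/32 = 62.5% of full dose.
- Grade 1 row: 32/32 = 100%.
- Ratio: 1/0.625 = 1.6.

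The subject would be getting the scheduled dose when a reduction was due; this is not an overdose. Hypotension that resolves within 8 hours triggers no AMG 330 step under either row.

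**5. Pembrolizumab hold.** It matters only if a dose falls due during the event. Days from the preceding AMG 330 step to pembrolizumab in cycle 1 (Protocol Tables 4-1 and 4-3):
- Cohort 1: day 8 to 15, 29 to 36 and 50 to 57 = 7 days each; day 64 to 78 = 14 days.
- Cohort 2: day 15 to 22 and 36 to 43 = 7 days each.

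These gaps are nominal. The footnote to Table 6-2 allows pembrolizumab up to 3 days early from its second cycle, so a 7-day gap could become 7 − 3 = 4 days if that window applies. Section 8.1.2 gives only ±1 day for cycle 1 visits.

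**6. How many subjects.** The documents give no frequency of fluid-treated hypotension, so this is an assumption with a range. Section 4.3 reports CRS in 31 of 49 monotherapy subjects, 63.3%. Applied to 20 subjects: 0.633 × 20 = 12.7. If fluid-treated hypotension is the only grade 2 feature in 5%, 10% or 25% of these, the counts are 0.6, 1.3 or 3.2. No probability of site error is applied, so these are upper bounds under each assumption.

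**7. DLT rule.** Section 6.2.1 counts grade 2 CRS not resolved to grade 1 within 7 days. Misgrading changes this count only if fluid-treated hypotension is the sole grade 2 feature beyond day 7.

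**The case against.** The strongest reply is that grading is already settled. The severity column governs, and a treatment example in another column is not a rival definition. Harm requires a site to grade backwards from the treatment cell, and nothing shows how often that would happen. This stands as a limit on likelihood. It does not make the example right, because sites are sent to the whole table for both grading and management.

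A second reply is that grade 1 could mean oral fluids or borderline pressure, since the grade 2 cell specifies intravenous fluids below 100 mmHg. That fails: the grade 2 criterion has no threshold, and grade 1 severity never mentions hypotension.

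Third, there are real safeguards:
- Section 6.2.2.1 calls its criteria general guidelines and permits dose changes for lower-grade events on judgement and in consultation with the sponsor.
- Section 6.2.1 requires sponsor approval for each next step.
- Subjects are in hospital for at least 72 hours after each step (Section 6.1.1.2), and both rows require the same minimum monitoring frequency.
- The dose level review sees vital signs, concomitant medication and adverse events (Appendix 3).
- Footnote c of Table 6-5 allows additional therapy.

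These make an error more visible and leave room for correct care, but they do not tell a site that the grade 1 example is wrong.

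Finally, the 1.6 ratio applies to a narrow subset. Hypotension that persists despite fluids would probably need a vasopressor, which already points to grade 2. The ratio describes subjects held only by continuing fluids. That qualification is fair.

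**Conclusion.** The concern holds. The grade 1 example is wrong as written, and it sits in an operative safety table. The correct grade can be worked out from the documents, so the defect is an invitation to error, not an unresolvable rule.

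Per affected subject, the tocilizumab dose to consider is halved, the pembrolizumab hold is missing, and the recorded grade is 1 instead of 2. Where fluids are still needed at 8 hours, AMG 330 over 32 hours is 100% instead of 62.5% of full dose. The number affected is unknown; the range of 0.6 to 3.2 of 20 subjects rests entirely on the assumed 5% to 25% and on CRS being as frequent as on monotherapy.

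An effect on the 7-day DLT criterion is possible but unlikely. Any-grade CRS incidence, the grade 3 and above tables, and the grade 3 and 4 CRS DLT criteria are unaffected. The change should be made, at modest severity.

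**What to change.** Delete the hypotension example from the grade 1 intervention cell of Table 6-5 and leave the grade 2 description as it is. Tell sites in a short memo that CRS hypotension needing fluids is at least grade 2 and is managed by the grade 2 row. A sentence stating that the severity column sets the grade would help but is optional.

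The cost is three words in one table and a memo. It needs no additional data or subjects, and no rule is lost because the grade 2 row already covers fluid-treated hypotension.

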9.1 Statistical Hypotheses

This is a phase 1 study and no formal statistical hypothesis will be tested.

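### The tumor lysis section pairs a uric acid threshold of 450 µg/L with 7.5 mg/dL, which is 75 000 µg/L, and the prophylaxis sentence carries only the µg/L figure

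*Protocol*

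**What the plan says.** The relevant text is in Protocol Section 6.8, in the part on tumor lysis syndrome. It first sorts subjects by white blood cell count: below 10 000/µL is low risk, 10 000 to 50 000/µL intermediate, and above 50 000/µL high. It then recalls the enrolment ceiling: "This protocol requires that subjects have a maximum WBC count of 15 000" per µL. That agrees with exclusion criterion 225 in Section 5.2.

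Two consecutive paragraphs then use uric acid.

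- **Risk features.** The sentence opens "Additional high risk features include baseline uric acid", sets the cut-off at more than 450 µg/L, and continues from that unit with "g/L (7.5 mg/dL), serum creatinine > 1.4 mg/dL, and lactate dehydrogenase (LDH) greater than the upper limit of normal (ULN". The figure in µg/L comes first, and the mg/dL figure follows in parentheses as its equivalent.
- **Prophylaxis.** The next paragraph opens "Patients with intermediate risk WBC count and elevated baseline uric acid (> 450 μ" (the unit is again µg/L), adds serum creatinine above 1.4 mg/dL as an alternative, and ends "or LDH greater than ULN will be recommended to receive allopurinol prophylaxis". It gives no mg/dL figure for uric acid. It also says that prophylaxis should start 3 days before the first dose of study drug.

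No other part of the protocol restates or corrects the threshold. Uric acid appears again only as a chemistry analyte in Table 11-1, and hyperuricaemia is listed among the anticipated serious adverse events in Section 11.8. The SAP does not mention the threshold.

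**The concern.** A threshold written in one unit with a second unit in parentheses tells the reader that the two figures are interchangeable. Here both units are mass per volume, so the pairing can be tested by powers of ten alone, and it fails by more than two orders of magnitude.

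The prophylaxis sentence makes this more than a slip in background text. It is the sentence a site would apply at screening, and it carries only one of the two figures. A site that works from it, with a laboratory report in mg/dL, would convert 450 µg/L to 0.045 mg/dL. A site that looks back one paragraph would use 7.5 mg/dL. The same rule could therefore be applied differently across the approximately 5 sites planned in Section 4.2.2. What is at stake is consistent use of a supportive-care recommendation, not any estimate or test.

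**Working it through.** **Inputs, all from Protocol Section 6.8 unless marked**

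- First figure in the risk-feature sentence: 450 µg/L.
- Parenthetical figure in the same sentence: 7.5 mg/dL.
- Figure in the prophylaxis sentence: 450 µg/L only.
- Intermediate white-cell band: 10 000 to 50 000/µL, with an enrolment maximum of 15 000/µL.
- Assumption, not in the documents: molar mass of uric acid 168.11 g/mol, varied from 165 to 171.

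**Step 1. Try to reproduce the stated equivalence.** With 10 dL in 1 L and 1000 µg in 1 mg, the concentration in µg/L is the concentration in mg/dL × 10 × 1000.

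- 7.5 mg/dL × 10 × 1000 = 75 000 µg/L, not 450 µg/L.
- In reverse, 450 µg/L ÷ 1000 ÷ 10 = 0.045 mg/dL, not 7.5 mg/dL.
- Ratio: 75 000 ÷ 450 = 166.7.

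The stated equivalence is not reproduced, and rounding cannot account for a factor of about 167.

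**Step 2. Look for a reading under which the pair agrees.** Suppose 450 is a molar concentration. Then µmol/L = (mg/dL × 10) ÷ (molar mass in g/mol) × 1000.

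- At 168.11 g/mol: 75 ÷ 168.11 × 1000 = 446 µmol/L.
- At 165 g/mol: 75 ÷ 165 × 1000 = 455 µmol/L.
- At 171 g/mol: 75 ÷ 171 × 1000 = 439 µmol/L.
- In reverse, at 168.11 g/mol: 450 × 168.11 ÷ 10 000 = 7.57 mg/dL.

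At the central value, 446 is within 1% of 450 (4 ÷ 450 = 0.9%). Under this assumption the pair agrees and only the unit label is out of line.

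**Step 3. Direction of the literal reading.** Since 0.045 is below 7.5, every subject above 7.5 mg/dL is also above 0.045 mg/dL. Applying the µg/L figure as printed keeps everyone whom the mg/dL figure would select and may add others. It removes no one.

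**Step 4. Who can be affected.** The enrolment ceiling narrows the intermediate band to 10 000 to 15 000/µL. Within it, a subject with creatinine above 1.4 mg/dL or LDH above the upper limit of normal is recommended prophylaxis whatever the uric acid unit. The unit matters only for subjects in that band who meet neither of the other two triggers and whose uric acid lies above 0.045 mg/dL but not above 7.5 mg/dL. The documents do not say how many of the approximately 20 planned subjects that would be.

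**Step 5. Any route into the statistics.** On hypotheses, Protocol Section 9.1 says "This is a phase 1 study and no formal statistical hypothesis will be tested". The uric acid cut-off appears in none of the DLT definition (Section 6.2.1), the eligibility criteria (Sections 5.1 and 5.2), the interim rule (Protocol Section 9.4.1.1, SAP Section 7.1) or the SAP analyses.

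**The case against.** The strongest case on the other side is that no careful reader would be misled. The mg/dL figure stands one paragraph earlier under the same heading. Both sentences use the number 450 with the same creatinine and LDH companions, and the second sentence describes the uric acid as elevated. Step 2 also gives a simple explanation. On this view it is an editorial slip in a recommendation that reaches few subjects.

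Much of that stands. It limits the weight of the point and makes a unit-label error the likely cause. It does not remove the inconsistency: the sentence a site would apply still carries a figure about 167 times lower than its pair. A fault in the reading of the PDF is unlikely, because the µg/L unit appears in two separate sentences.

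Four stronger readings are tempting, and the documents do not support them.

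- A reader might infer that the protocol holds two rival cut-offs. It presents one threshold in two notations, one of which does not fit the other.
- A reader might infer that the mg/dL figure is the right one. The conversion shows only that the pair is inconsistent. The choice is a clinical matter.
- A reader might infer that, taken literally, the criterion would no longer separate higher-risk from lower-risk subjects. That needs the range of serum uric acid in this population, which neither document gives.
- A reader might infer that subjects could miss prophylaxis if the µg/L figure is applied as printed. Step 3 shows the opposite direction.

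**Conclusion.** The point holds as an inconsistency between a unit and its paired value. The 167-fold size follows from the printed figures alone, with no assumption. The explanation as a unit-label error is probable but rests on a molar mass that the documents do not give; across 165 to 171 g/mol the paired value is 455 to 439 µmol/L.

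The practical weight is low, for the reasons in Steps 3 to 5: a recommendation with two other triggers, a narrow white-cell band, an effect in one direction only, and no bearing on sample size, the stopping rule or any analysis. It is worth correcting because the figure sits in a sentence that sites act on, not because it threatens the trial's conclusions.

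**What to change.** The sponsor should reconcile the two expressions in Protocol Section 6.8 and state one threshold, in one consistent unit, in both the risk-feature sentence and the prophylaxis sentence. If a second unit is kept in parentheses, it should be a checked conversion and appear in both places. Which value applies is for the sponsor and investigators, and this review takes no position on it.

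The cost is an edit to two sentences in one section, which could go into the next protocol amendment with a short clarification to sites in the meantime. The SAP needs no change.
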